2. SUMMARY OF KEY PROTOCOL INFORMATION

2.1. Changes to the Protocol Defined Statistical Analysis Plan

Any changes from the originally planned statistical analysis specified in the protocol GlaxoSmithKline Document Number 2015N256437_00 are outlined in Table 1.

Protocol		Re	porting & Analysis Plan		
Statistic	al Analysis Plan	Sta	tistical Analysis Plan	Ra	tionale for Changes
• Time deteri	to clinically important ioration composite endpoint	•	Time to clinically important deterioration composite endpoint will not be analysed	•	Study deemed too short to assess and SGRQ is not collected.
 Propo accor ≥1 ur from 	ortion of responders ding to CAT (defined as a hit improvement in score baseline) at Weeks 4 and 8	•	Proportion of responders according to CAT (defined as a ≥ 2 unit improvement in score from baseline) at Weeks 4 and 8	•	Typographical error
 ITT p All rai exclu rando who i run-ir rando be rai other rando consi rando Displa treatr was r 	opulation definition ndomized subjects, ding those who were omized in error. A subject s recorded as a screen or a failure and also omized will be considered to ndomized in error. Any subject who receives a omization number will be dered to have been omized. ays will be based on the nent to which the subject andomized.	•	ITT population definition now includes – received at least one dose of study medication. All randomized subjects, excluding those who were randomized in error and received at least one dose of study medication. A subject who is recorded as a screen or run-in failure and also randomized will be considered to be randomized in error. Any other subject who receives a randomizet on have been randomized. Displays will be based on the treatment to which the subject was randomized.	•	For consistency with prior GSK573719 + GW642444 studies
• No In	haler Naive population	•	Inhaler Naive population definition All subjects in the ITT population who have not used either Ellipta or Respimat for 6 months prior to inhaler evaluation (Visit 2	•	Population for Inhaler summaries and analysis

Table 1 Changes to Protocol Defined Analysis Plan

Protocol	Reporting & Analysis Plan	
Statistical Analysis Plan	Statistical Analysis Plan	Rationale for Changes
	 or Visit 5). This population will be used for all Inhaler assessment displays unless stated otherwise. 	

2.2. Study Objective(s) and Endpoint(s)

Objectives	Endpoints			
Primary Objectives	Primary Endpoint			
To compare the effect of UMEC/VI 62.5/25 mcg with TIO/OLO 5/5mcg once daily on lung function in subjects with moderate COPD over 8 weeks of treatment.	 Trough FEV₁ at Week 8 			
Other Efficacy Objectives	Other Efficacy Endpoints			
To compare the effect of UMEC/VI 62.5/25 mcg with TIO/OLO 5 /5mcg on other measures of efficacy and measures of health-related quality of life	 Proportion of responders according to FEV1 (a responder is defined as a ≥100mL change in Trough FEV₁ from baseline) at Week 8 Rescue albuterol/salbutamol use (percentage of rescue-free days and mean number of Inhalations/day) captured in e diary Trough FEV₁ at Week 4 Trough FVC at Weeks 4 and 8 COPD Assessment Test (CAT) score at Weeks 4 and 8 COPD Assessment Test (CAT) score at Weeks 4 and 8 Proportion of responders according to CAT (defined as a ≥2 unit improvement in score from baseline) at Weeks 4 and 8 Inhaler ease of use Inhaler errors Assessment of respiratory daily symptoms over Weeks 1-8 using Evaluating Respiratory Symptoms - COPD (E-RS) and its subscales (breathlessness, cough and sputum and chest symptoms) 			
Exploratory Objectives	Exploratory Endpoints			
 To compare the effect of UMEC/VI 62.5/25 mcg with TIO/OLO 5 /5mcg on other measures of efficacy and measures of health-related quality of life 	 Rescue albuterol/salbutamol use (percentage of rescue- free days and mean number of Inhalations/day) over Weeks 1-8 might using eMDI 			
Safety	Safety Endpoints			
 To evaluate safety and tolerability of UMEC/VI 62.5/25 mcg and TIO/OLO 5/5mcg 	 Incidence of adverse events (AEs) Incidence of COPD exacerbations 			

2.3. Study Design

2.4. Statistical Hypotheses

The null hypothesis is that the difference in trough FEV_1 between treatment groups is less than or equal to a pre-specified non-inferiority margin Δ :

H₀: $T_1 - T_2 \leq \Delta$

The alternative hypothesis is that the difference between treatment groups is greater than the margin.

 $H_1: T_1 - T_2 > \Delta$

where T_1 and T_2 are the treatment means for UMEC/VI 62.5/25 mcg and TIO/OLO 5/5 mcg, respectively.

CONFIDENTIAL

The non-inferiority margin has been set at -50mL, which is consistent with the noninferiority margins used for trough FEV_1 or 0 to 24 hour weighted mean FEV_1 in previous studies comparing long-acting bronchodilators or long-acting bronchodilator/ICS combinations [Ichinose M, 2010; Vogelmeier C, 2010; Agustí A, 2014].

If the lower bound of the two-sided 95% confidence interval around the (UMEC/VI 62.5/25 mcg vs. TIO/OLO 5/5 mcg) treatment difference is above -50mL then UMEC/VI 62.5/25 mcg will be considered non-inferior to TIO/OLO 5/5 mcg.

If the lower bound of the two-sided 95% confidence interval around the (UMEC/VI 62.5/25 mcg vs. TIO/OLO 5/5 mcg) treatment difference is above 0 then UMEC/VI 62.5/25 mcg will be considered superior to TIO/OLO 5/5 mcg.

P-values will be displayed in the analysis outputs in this study. Inference to be drawn from these p-values will be as follows:

- If the treatment comparison on the primary endpoint has a lower confidence limit below the non-inferiority margin, non-inferiority is not demonstrated. No inference will be drawn from p-values for treatment comparisons on any other endpoints.
- If the treatment comparison on the primary endpoint has a lower confidence limit above the non-inferiority margin but below 0, non-inferiority is established but the p-value cannot be used to give an indication of the strength of that noninferiority. Note the p-value is for a test of superiority and not associated with a test for non-inferiority.

Inference will be drawn from p-values for treatment comparisons on non lungfunction related endpoints (see below), which will be called statistically significant if <0.05. If the treatment comparison on the primary endpoint has a lower confidence limit above 0, superiority is established and the p-value can be used to give an indication of the strength of that superiority. Inference will be drawn from p-values for treatment comparisons on all other endpoints, which will be called statistically significant if <0.05.

The primary endpoint of trough FEV_1 is considered independent of non lung function 'other' endpoints, defined as rescue medication use, CAT score, inhaler ease of use, inhaler errors, respiratory daily symptoms endpoints. All other endpoints are lung function endpoints and are not considered to be independent from the primary endpoint of trough FEV_1 .

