8.1.2. Planned Efficacy Statistical Analyses for Other Efficacy Endpoints

8.1.2.1. Responder FEV₁

Statistical Analyses for Proportion of Trough FEV₁ Responders Endpoints

• Proportion of responders according to FEV₁ (a responder is defined as a ≥100mL change in Trough FEV₁ from baseline)

Model Specification

- At each visit, the proportion of subjects achieving a ≥100mL change in Trough FEV₁ from baseline will be analysed using a generalised linear mixed model.
- The following covariates will be included in the model: period baseline, mean baseline, period, treatment, visit, visit by period baseline, visit by mean baseline and visit by treatment interactions, where visit is nominal.

Example SAS code

proc glimmix data=start; class subject period treatment visit; model endpoint(descending)=period treatment visit mean_base period_base visit*period_base visit*mean_base visit*treatment / dist=binary link=logit ddfm=kr solution; random intercept / subject=subject; random visit / subject=subject*period residual type=un; lsmeans visit*treatment / diff;

ods output Ismeans=Ismeans;

ods output diffs=diffs;

run;

Statistical Analyses for Proportion of Trough FEV₁ Responders

• Note: The residual statement turns the random statement into a repeated statement

Model Checking & Diagnostics

• Refer to Appendix 11: Model Checking and Diagnostics for Statistical Analyses.

Model Results Presentation

The odds ratio, 95% CI and p-value of UMEC/VI 62.5/25 vs. TIO/OLO 5/5 will be presented.

Summary Results Presentation

• The number and percentage of responders and non-responders at each visit will be summarized on the same table as the analysis results detailed above.

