8.1.2.5. E-RS

Sta	Statistical Analyses for E-RS						
En	Endpoints						
•	Change from baseline in weekly mean scores for E-RS and its subscales (breathlessness, cough and sputum and chest symptoms)						
Мо	Model Specification						
•	E-RS endpoint above will be analyzed using similar methodology as the MMRM analysis of Trough FEV ₁ (detailed in Section 7.1.2) using all available data recorded from the EXACT-PRO questionnaire.						

• For E-RS and subscales, all weekly mean scores will be included in the analysis. Model Checking & Diagnostics

Sta	atistical Analyses for E-RS
•	Refer to Appendix 11: Model Checking and Diagnostics for Statistical Analyses.
Мо	odel Results Presentation
•	Least squares (LS) mean and LS mean changes from baseline with their corresponding standard errors (SEs) will be presented for each treatment by weekly treatment period, together with estimated treatment differences (UMEC/VI 62.5/25 vs. TIO/OLO 5/5), corresponding 95% CIs and p-values.
Su	mmary Results Presentation
•	The mean score at baseline and during each week of treatment will be summarized by treatment. The change from baseline values will also be summarized by treatment, for each week of treatment.
Sta	atistical Analysis of Proportion of Responders according to E-RS
En	dpoints
•	Proportion of responders for E-RS and its subscales (breathlessness, cough and sputum and chest symptoms)
Мо	odel Specification
•	For each mean weekly E-RS total score and subscales, the proportion of responders will be analyzed using similar methodology as the generalized linear mixed model analysis of Trough FEV ₁ responder (detailed in Section 8.1.2.1).
•	Please see Section 10.6.4 for details on responder definitions.
•	See Section 10.7.2 for details on how to handle missing data.
Мо	odel Checking & Diagnostics
•	Refer to Appendix 11: Model Checking and Diagnostics for Statistical Analyses.
Мо	odel Results Presentation
•	The odds ratio, 95% CI and p-value of UMEC/VI 62.5/25 vs. TIO/OLO 5/5 will be presented
Su	mmary Results Presentation
•	The number and percentage of responders and non-responders at each visit will be summarized on the same table as the analysis results detailed above.

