10.10. Appendix 10: Multiple Comparisons & Multiplicity

10.10.1. Handling of Multiple Comparisons & Multiplicity

See Section 2.4 for details on inferences that can be drawn on primary and 'other' endpoints for non-inferiority and superiority.

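### After non-inferiority, SAP 2.4 calls any non-lung-function p-value below 0.05 statistically significant, with no control across at least 42 of them and no named E-RS result

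*SAP*

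**What the plan says.** SAP 2.4 has three branches. If non-inferiority fails, nothing is inferred on any other endpoint. If non-inferiority holds without superiority, inference extends to non-lung-function "endpoints (see below), which will be called statistically significant if <0.05". If superiority also holds, it extends to "treatment comparisons on all other endpoints, which will be called statistically significant if <0.05".

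The last paragraph of SAP 2.4 sorts the endpoints. Trough FEV1 "is considered independent of non lung function 'other' endpoints", which are listed as rescue use, CAT score, ease of use, inhaler errors and daily respiratory symptoms. It then adds: "All other endpoints are lung function endpoints and are not considered to be independent" of the primary. Both statements relate an endpoint to the primary; neither relates these endpoints to one another. The multiplicity appendix (SAP 10.10.1) only refers back: "See Section 2.4 for details on inferences that can be drawn on primary and" the other endpoints.

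For E-RS, SAP 8.1.2.5 follows the primary MMRM. For the total and three subscales, LS means "will be presented for each treatment by weekly treatment period, together with estimated treatment differences", with confidence intervals and p-values. On responders it says "For each mean weekly E-RS total score and subscales, the proportion of responders will be analyzed" with the model of SAP 8.1.2.1, whose code requests "lsmeans visit*treatment / diff". No week and no combined effect is named as the E-RS result. Rescue use, also a diary endpoint, gets one overall treatment effect (SAP 8.1.2.3).

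**The concern.** The non-inferiority gate decides when this family opens. It does not limit error inside the family. P-values shown only for description would raise little concern, but SAP 2.4 says that inference is drawn and assigns the label to each p-value separately.

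Followed exactly, the plan lets one isolated week on one E-RS subscale be reported as a statistically significant treatment difference, in an open-label head-to-head trial. Nothing in the SAP would require the report to say that it was one of 32 such comparisons. What is at stake is the credibility of claims on symptoms, health status, rescue use and device handling.

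**Working it through.** **1. The plan's own figure.** The documents state no error rate for this family. The figure that bears on it is the power of the gate (Protocol 9.2.1): 168 evaluable subjects, within-subject SD 140 mL, margin -50 mL, true difference 0, one-sided 2.5%.

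- SE = 140 × √(2/168) = 15.28 mL
- 50/15.28 - 1.960 = 1.313, giving power 0.906 (0.902 with the t distribution)

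The stated 90% is reproduced. Under the plan's own assumptions the family therefore opens about nine times in ten.

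**2. Count of p-values.** The documents give no count; this one is ours.

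| Endpoint | Source | p-values |
|---|---|---|
| E-RS means: 4 scores × 8 weeks | SAP 8.1.2.5 | 32 |
| CAT score, Weeks 4 and 8 | SAP 8.1.2.4 | 2 |
| eDiary rescue use: puffs/day, rescue-free days | SAP 8.1.2.3 | 2 |
| Ease of use: six questions, one test each | Protocol 7.4.4.1; SAP 8.1.2.6 | 6 |
| **Narrow total** | | **42** |
| CAT responders, Weeks 4 and 8 | SAP 8.1.2.4 | 2 |
| E-RS responders: 4 scores × 8 weeks (inferred) | SAP 8.1.2.5 with 8.1.2.1 | 32 |
| **Wide total** | | **76** |

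eMDI rescue use and inhaler errors are summarised without tests, so they add none. The raw and change-from-baseline models are counted once: period baseline plus mean baseline equals baseline, so the treatment difference is the same in both.

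**3. Superiority branch.** Lung-function p-values are FEV1 at Week 4 (1), FEV1 responders (1 by SAP 2.2, 2 by SAP Table 5), FVC (2) and IC (2), so 6 to 7.

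- From the wide reading: 76 + 6 to 7 = 82 to 83.
- From the narrow reading, the 34 responder p-values enter here too: 42 + 34 + 6 to 7 = 82 to 83, that is, 40 to 41 more.

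**4. Expected false positives.** With no true differences and the gate open, the expected number is k × 0.05 whatever the correlation among the tests:

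- 42 × 0.05 = 2.1 (1.05 of them favouring UMEC/VI)
- 76 × 0.05 = 3.8 (1.9 favouring UMEC/VI)
- without ease of use, where two different inhalers may truly differ: 36 × 0.05 = 1.8

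No rate is given for the lung-function endpoints, because a complete null is implausible once FEV1 superiority has been shown.

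**5. Chance of at least one.** Independence gives 1 - 0.95^42 = 0.884 and 1 - 0.95^76 = 0.980, but weekly scores on one scale are correlated and the documents give no values. Two sets of assumed correlations were simulated, with 100,000 draws per setting:

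- Set A: 0.5 to 0.9 within an endpoint, 0 to 0.4 between endpoints.
- Set B: 0.6 to 0.9 between weeks, 0.5 or 0.7 between E-RS scales, 0.5 to 0.9 within the other families, 0 or 0.35 between E-RS, CAT and rescue use, and 0.6 between mean and responder.

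| Tests | Set A | Set B | Combined |
|---|---|---|---|
| 42 | 0.448-0.795 | 0.428-0.709 | about 0.43-0.80 |
| 76 | 0.508-0.906 | 0.568-0.858 | about 0.51-0.91 |

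For one E-RS scale over eight weeks, the chance that some week falls below 0.05 is about 0.30, 0.22, 0.16, 0.12 and 0.09 at week correlations of 0.3, 0.6, 0.8, 0.9 and 0.95. One overall contrast has 0.05.

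**6. What an overall E-RS contrast does alone.** If four contrasts replaced the weekly and responder tests, 4 + 2 + 2 + 6 = 14 tests would remain. The expected number is 14 × 0.05 = 0.7, and the chance of at least one is about 0.31 to 0.46 over the same assumptions. The wording of SAP 2.4 must change as well.

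**The case against.** The strongest reply is that these endpoints sit below the primary, that the SAP does pre-specify a gate, and that strict error control among endpoints of this class is a reporting convention. Every weekly difference is tabulated with a 95% interval and the weekly E-RS means are plotted (Figures 2.10-2.13), so no week is hidden. This stands as a limit on the consequence. It does not remove the label, which applies to each p-value alone.

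Stronger readings are tempting, and the documents do not support them:

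- *Weekly E-RS results contradict the stated endpoint.* SAP 2.2 speaks of symptoms assessed over Weeks 1-8. It does not promise a mean or a single contrast. SAP 8.1.2.5 defines the endpoint through weekly mean scores, and SAP 10.6.4 sets weekly windows. A weekly profile satisfies this. Rescue use shows a different choice, not a rule that E-RS breaks.
- *A false positive is nearly certain.* The 0.884 figure needs independent tests. The simulated ranges are illustrations too. Only the expected counts are free of correlation assumptions.
- *There are 76 tests beyond doubt.* Weekly responder testing is a reasonable inference from the model text and code. However, the titles of Tables 2.37-2.40 name no week, and the responder results line asks for an odds ratio without one.
- *CAT responders belong with lung function.* The closing sentence of SAP 2.4 says so if read literally, but SAP 10.6.4 derives responder status from the CAT score. This needs a clarification and would not be a finding by itself.

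**Conclusion.** The concern holds as a matter of labelling. SAP 2.4 attaches a claim of statistical significance to each of at least 42 p-values, with no control among them, and 2.1 are expected below 0.05 if there are no true differences (3.8 on the reading with 76). These figures rest on our count, on a complete null and on the gate having opened. The chance of at least one, about 0.43 to 0.80 for 42 tests, also rests on assumed correlations and should be quoted only as an illustration.

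A reader might infer that the primary conclusion is compromised. It is not: the non-inferiority and superiority tests on trough FEV1 come first and are unaffected. The absence of a named E-RS result is a gap worth closing cheaply, not an error in the endpoint.

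**What to change.** 1. **SAP 2.4, in both the non-inferiority and superiority branches.** Replace the rule for other endpoints with a statement that their p-values are nominal and not adjusted for multiplicity. Alternatively, limit formal claims to a short ordered list, chosen by the sponsor and fixed before database freeze.
2. **SAP 8.1.2.5.** From the MMRM already planned, add one Weeks 1-8 treatment contrast for E-RS total and each subscale, and name it as the E-RS result. State the weights (1/8 per week), because this model has a week-by-treatment term and the rescue model does not. Keep weekly and responder results as supportive estimates with 95% intervals, and show any p-values that remain as nominal only.
3. **Optional clarification in SAP 2.4.** Say whether CAT and E-RS responder analyses count as non-lung-function endpoints.

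The cost is SAP wording, four contrasts from existing models and one extra row in each of Tables 2.33-2.36. No new data are needed. The downside is that fewer results can be labelled significant.

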3. OBJECTIVE(S) AND ENDPOINT(S)

	Objectives		Endpoints
Pri	mary		
•	To compare the effect of UMEC/VI 62.5/25 mcg with TIO/OLO 5/5mcg once daily on lung function in subjects with moderate COPD over 8 weeks of treatment.	•	Clinic visit trough FEV ₁ at Week 8
Ot	hers		
•	To compare the effect of UMEC/VI 62.5/25 mcg with TIO/OLO 5 /5mcg on other measures of efficacy and measures of health- related quality of life	•	Proportion of responders according to FEV₁ (a responder is defined as a ≥100mL change in Trough FEV₁ from baseline) at Week 8 Rescue albuterol/salbutamol use (percentage

Objectives	Endpoints			
	 of rescue-free days and mean number of Inhalations/day) captured in e diary Trough FEV₁ at Week 4 Trough FVC at Weeks 4 and 8 Trough IC at Weeks 4 and 8 COPD Assessment Test (CAT) score at Weeks 4 and 8 Proportion of responders according to CAT (defined as a ≥1 unit improvement in score from baseline) at Weeks 4 and 8 Time to clinically important deterioration composite endpoint Inhaler ease of use Inhaler errors Assessment of respiratory daily symptoms over Weeks 1-8 using Evaluating Respiratory Symptoms - COPD (E-RS) and its subscales (breathlessness, cough and sputum and chest symptoms) 			
Exploratory				
To compare the effect of UMEC/VI 62.5/25 mcg with TIO/OLO 5 /5mcg on other measures of efficacy and measures of health- related quality of life	 Rescue albuterol/salbutamol use (percentage of rescue-free days and mean number of Inhalations/day) over Weeks 1-8 using eMDI as data allow 			
To evaluate safety and tolerability of UMEC/VI 62.5/25 mcg and TIO/OLO 5/5mcg	 Incidence of adverse events (AEs) Incidence of COPD exacerbations 			

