8. OTHER STATISTICAL ANALYSES

8.1. Other Efficacy Endpoints

8.1.1. Overview of Planned Efficacy Analyses

The other efficacy summaries and analyses will be based on the ITT population, unless otherwise specified.

Table 5 provides an overview of the planned efficacy analyses, with further details of data displays being presented in Appendix 13: List of Data Displays.

Endpoint	Change from Baseline[1]						
		Stats Ana	lysis	Summary Indiv		vidual	
	Т	F	L	Т	F	F	L
Responder FEV ₁							
Proportion of	Y			Y			Y
responders according							
to FEV ₁ (a responder is							
defined as a ≥100mL							
change in Trough FEV ₁							
from baseline) at Week							
4 and 8 [2]							
Trough FVC and IC	r	•	1			· · · ·	
Trough FVC	Y	Y		Y			Y
Trough IC	Y	Y		Y			Y
Rescue medication							
Mean number of puffs	Y			Y			Y
per day of rescue over							
the study duration							
(Weeks 1-8) captured							
using e-diary							
Percentage of rescue	Y			Y			Y
free days over the							
study duration (Weeks							
1-8) captured using e-							
diary [2]							
Mean number of				Y			Y
occurrences per day of							
rescue over the study							
duration (Weeks 1-8)							
captured using e-MDI				X			
Percentage of rescue				Y			Y
free days over the							
study duration (Weeks							
1-8) captured using e-							
	N/		T				
CAT score	Y	Y Y		Y			Υ

Table 5Overview of Planned Efficacy Analyses

Endpoint	Change from Baseline[1]							
		Stats Ana	lysis	Sum	mary	Indiv	Individual	
	Т	F	L	Т	F	F	L	
Proportion of CAT	Y			Y			Y	
responders [2]								
Inhaler assessments								
Inhaler ease of use	Y			Y			Y	
Inhaler errors				Y			Y	
E-RS								
E-RS	Y	Y		Y			Y	
Proportion of E-RS	Y			Y			Y	
responders [2]								

NOTES :

- T = Table, F = Figure, L = Listing, Y = Yes display generated.
- Stats Analysis = Represents TFL related to any formal statistical analyses (i.e. modelling) conducted.
- Summary = Represents TFL related to any summaries (i.e. descriptive statistics) of the observed raw data.
- Individual = Represents TFL related to any displays of individual subject observed raw data.
- 1. Analysis and Summaries to include absolute values too for all endpoints with the exception of Responder analysis
- 2. Summary and analysis will be combined into a single display.
- 3. Summary only

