8.1.2.6. Inhaler assessment summaries

Inh	Inhaler Error Assessment							
En	dpoint							
•	Percentage of subjects making at least one critical error							
•	Percentage of subjects making at least overall error							
•	See Section 10.6.4 for error derivation.							
Su	Summary of Results Presentation							
٠	Summarized by inhaler, response (at least one error critical and overall) using n and %.							
	Results will be presented by sequence and total.							
•	The number and percent of subjects reporting each error for each individual question will also be presented (separate table for each inhaler).							

Sta	itistical Analysis of Inhaler Ease of Use Assessment
En	dpoints
•	Ease of use' rating for the ELLIPTA DPI compared with the Respimat.
Мо	del Specification
•	Each question will be analysed using the Cochran-Mantel-Haenszel test adjusted for country The Cochran-Mantel-Haenszel test serves as a stratified approximation to Prescott's test a
•	variation of a one-sample chi-square test that accounts for study inhaler sequence and difference in ease of use response [Prescott, 1981; Senn, 2002]. Homogeneity among country with respect difference in to ease of use will be assessed using a Breslow-Day test. Results of this test will not be reported on the final data display. See Section 10.6.4 for ease of use derivation.
Exa	ample SAS code
•	SAS code for stratified approximation to Prescott's test for each preference question:
•	ods output CMH = cmhi (where = (upcase(AltHypothesis) =: 'ROW MEAN SCORES') keep = AltHypothesis Prob) ; proc freq data = pref_data ; tables country * seq * ease_ord / cmh ;
	run ;
•	SAS code for checking brestow-Day rest for 2x2
	proc freq data = pref_data (where = (ease_ord ne 0)) ; tables country * seg * ease_ord / cmb :
Мо	del Results Presentation
•	P-values will be presented for the comparison between inhalers on the summary table
Su	mmary Results Presentation
•	Responses to the Ease of Use questionnaire will be summarised by inhaler, question/item
	and type of responses for the IN population.
•	The percentage preference (rated higher for Ellipta, rated higher for Respimat, rated the same) will be summarized on the same table as the analysis results detailed above. Results will be
	presented by question, sequence and total.
•	An additional summary will be produced based on the difference between the ratings for
	the two inhalers. The rating are coded as Very Easy=1, Easy=2, Neutral=3, Difficult=4,

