			Weeks 1-8 using e-diary					
2.24.	ITT	E_T09	Summary of Mean Number of Puffs of Rescue Medication per Day using eMDI		SAC			
2.25.	ITT	E_T11	Summary of Percentage Rescue-free Days using eMDI		SAC			
CAT								
2.26.	ITT	E_T02	Summary of CAT Score	Include baseline	SAC			
2.27.	ITT	E_T03	Analysis of CAT Score		SAC			
2.28.	ITT	E_T08	Summary and Analysis of Proportion of Responders According to CAT		SAC			
E-RS								
2.29.	ITT	E_T02	Summary of Weekly Mean E-RS Total Score		SAC			
2.30.	ITT	E_T02	Summary of Weekly Mean E-RS - Breathlessness Score		SAC			
2.31.	ITT	E_T02	Summary of Weekly Mean E-RS - Cough and Sputum Score		SAC			
2.32.	ITT	E_T02	Summary of Weekly Mean E-RS - Chest Score		SAC			
2.33.	ITT	E_T03	Analysis of Weekly Mean E-RS Total Score		SAC			
2.34.	ITT	E_T03	Analysis of Weekly Mean E-RS - Breathlessness Score		SAC			
2.35.	ITT	E_T03	Analysis of Weekly Mean E-RS - Cough and Sputum Score		SAC			
2.36.	ITT	E_T03	Analysis of Weekly Mean E-RS - Chest Score		SAC			
2.37.	ITT	E_T08	Summary and Analysis of Proportion of Responders According to E-RS Total Score		SAC			

Efficacy: Tables								
No.	Population	IDSL / TST ID / Example Shell	Title	Programming Notes	Deliver-able			
2.38.	ITT	E_T08	Summary and Analysis of Proportion of Responders According to E-RS Breathlessness Score					
2.39.	ITT	E_T08	Summary and Analysis of Proportion of Responders According to E-RS Cough and Sputum Score		SAC			
2.40.	ITT	E_T08	Summary and Analysis of Proportion of Responders According to E-RS Chest Score		SAC			
Inhaler Ease of use								
2.41.	IN	(example 200301)	Summary of Ease of Use Questionnaire		SAC			
2.42.	IN	(example 200301)	Summary and Analysis of Ease of Use Rating	Present by sequence and total	SAC			
2.43.	IN	(example 200301)	Summary of Ease of Use Rating	Present by sequence and total (example 200301)				
Inhaler Er	rors							
2.44.	IN	(example 200301)	Summary of Errors for the ELLIPTA Inhaler	Raw questionnaire data	SAC			
2.45.	IN	(example 200301)	Summary of Errors for the Respimat Inhaler	Raw questionnaire data	SAC			
2.46.	IN	(example 200301)	Summary of Number of Subjects with at least One Error	Include critical and overall. Present by sequence and total	SAC			

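### SAP 2.4 counts inhaler errors among the endpoints that carry p-value inference, but the SAP plans only counts and percentages for them

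*SAP*

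**What the plan says.** **The inference rule.** SAP 2.4 covers the case where non-inferiority is shown but superiority is not: "Inference will be drawn from p-values for treatment comparisons on non lungfunction related endpoints", "which will be called statistically significant if <0.05". The section then lists those endpoints, "defined as rescue medication use, CAT score, inhaler ease of use, inhaler errors, respiratory daily symptoms endpoints". If superiority is shown, the rule widens to every other endpoint, which again takes in errors. If non-inferiority fails, no inference is drawn on any of them.

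**The planned output for errors.** SAP 8.1.2.6 names two endpoints: the percentage of subjects with one or more critical errors, and the percentage with one or more errors of any kind. The results are "Summarized by inhaler, response (at least one error critical and overall) using n and" %, by sequence and in total, with n and % per checklist item. There is no model specification. In SAP Table 5 the row for errors marks only a summary table and a listing. The columns left blank are explained in the table notes: "Stats Analysis = Represents TFL related to any formal statistical analyses (i.e. modelling) conducted". In SAP 10.13.5, Table 2.46 is titled "Summary of Number of Subjects with at least One Error".

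**The neighbouring endpoint.** For ease of use, also in SAP 8.1.2.6, there is a Cochran-Mantel-Haenszel approximation to Prescott's test, SAS code and this output: "P-values will be presented for the comparison between inhalers on the summary table". Its Table 2.42 is titled as a summary and analysis.

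**The objective.** Protocol section 3 lists inhaler errors under an objective to compare the two treatments "on other measures of efficacy and measures of health- related quality of life".

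**The concern.** A rule that says which endpoints may be called statistically significant should match the analyses that are planned. Here it names one for which nothing testable is produced. That leaves two readings of a pre-specified rule: errors carry inference by a method nobody has written down, or errors are descriptive and the list is wrong. If a test were added after the data are seen, SAP 2.4 could be cited in its support although no method, population or pairing rule had been fixed.

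The second loss is the comparison itself. Inhaler errors are recorded at Visits 2 and 5, so a subject who reaches Visit 5 is observed on both devices. Two separate percentages do not show how often the same subject erred on one device and not the other, and that is what determines the uncertainty of the difference.

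**Working it through.** **Step 1: set the places side by side.**

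| Place | Ease of use | Inhaler errors |
|---|---|---|
| SAP 2.4 list for inference | named | named |
| SAP 8.1.2.6 model | CMH/Prescott, with code | none |
| SAP Table 5, formal analysis | marked | blank |
| SAP 10.13.5 | 2.42 summary and analysis | 2.44 to 2.46 summaries |
| SAP Table 1 (changes from protocol) | not mentioned | not mentioned |
| Protocol 9.4.1 | no test | no test |

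Three separate parts of the SAP agree that errors are summarised only, so the blank in Table 5 is not an artefact of a broken table. Protocol 9.4.1 is silent on both endpoints and settles nothing.

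**Step 2: can the planned percentages yield the interval?** The documents give no figure for errors to reproduce, because the sample-size sections concern trough FEV1 only. The inputs below are therefore assumptions. Let p1 and p2 be the proportions with an error on one device only and on the other only, and n the number of pairs.

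- Difference d = p1 − p2; discordance s = p1 + p2.
- 95% half-width = 1.96 × √((s − d²)/n).
- McNemar-type power, two-sided 0.05 = Φ((|d|√n − 1.96√s)/√(s − d²)).

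Suppose 30% err on one device and 20% on the other. If 15% err on both, then p1/p2 = 15%/5%. If 10% err on both, then p1/p2 = 20%/10%. The percentages and the 10-point difference are the same, but with n = 186:

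- 15%/5%: 1.96 × √((0.20 − 0.01)/186) = 0.063
- 20%/10%: 1.96 × √((0.30 − 0.01)/186) = 0.077

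So the planned table cannot supply the interval. The subject-level listings (40 to 42) could, but only by further work.

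**Step 3: illustrative range.** The figure 186 is borrowed from protocol 9.2.1 (subjects with a Week 8 assessment in the ITT population). It is not a count of subjects assessed for errors on both devices. The figure 100 stands for a smaller Inhaler Naive set and has no source in the documents.

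| Pairs | p1/p2 | Half-width (points) | Power |
|---|---|---|---|
| 186 | 5%/5% | 4.5 | – |
| 186 | 15%/5% | 6.3 | 87% |
| 186 | 20%/10% | 7.7 | 71% |
| 186 | 30%/10% | 8.6 | 99% |
| 100 | 5%/5% | 6.2 | – |
| 100 | 15%/5% | 8.5 | 61% |
| 100 | 20%/10% | 10.6 | 45% |
| 100 | 30%/10% | 11.8 | 90% |

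These are unstratified McNemar-type figures and do not give the power of the stratified test.

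**Step 4: who forms a pair?** SAP section 4 defines the Inhaler Naive population by no use of either device in the 6 months before the evaluation at Visit 2 or Visit 5. By Visit 5 a subject has been assigned one of the two devices for 8 weeks and then washed out for about 3, so that use began about 11 weeks earlier. Read literally, nobody treated in period 1 is naive at Visit 5. Yet the ease-of-use test in the same population needs ratings on both devices, which suggests that study-assigned use was not meant to count. The text should say so.

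**The case against.** The strongest reply is that SAP 2.4 promises no p-value. It opens by saying p-values will appear in the outputs and then states what may be inferred from them. The sentence listing errors sorts endpoints by whether they are considered independent of trough FEV1. On that reading an endpoint without a p-value simply has no inference, and the operative sections tell a programmer exactly what to produce. This reading is fair, and it rules out the inference that the SAP commits to a test and then drops it. It does not explain why errors are named in a list whose purpose is to say where inference will be drawn.

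Second, a reader might infer from ease of use that errors must be tested in the same way. The documents do not support that. Ease of use applies one five-point scale to both devices. The error checklists in SAP 10.6.4 differ: as far as the broken table can be read, Respimat has 14 scored rows, including cartridge loading and priming, against 9 for Ellipta. Having any error therefore depends partly on checklist length. Errors are also recorded by the investigator or designee in an open-label trial. Descriptive reporting is defensible if the SAP says that is the intention.

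Third, a reader might take the figures above as precision the trial is known to hold. They are not, since the rates, discordance and pair counts are all assumed.

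**Conclusion.** The mismatch stands on the text alone. SAP 2.4 includes inhaler errors in its inference rule, and no section produces a p-value, difference or interval for them. It is modest in weight: this is an 'other' endpoint, inference on it is conditional on non-inferiority, and nothing here touches the primary analysis, the sample size or the non-inferiority conclusion. The documents also do not show that a post hoc test will follow, only that the present wording would leave room for one.

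The correction is still worth making. The data are already collected, the method is already in the SAP for ease of use, and a paired difference with its interval serves an objective worded as a comparison better than two percentages do. Its size cannot be stated. Over the assumed inputs above, half-widths run from 4.5 to 11.8 points.

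**What to change.** Before database freeze, amend the SAP in one of two ways.

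**Preferred: specify the analysis.**
- In 8.1.2.6, for one or more critical errors and for one or more errors of any kind, add the within-subject difference in proportions (Ellipta minus Respimat) with its 95% CI, and the sequence-adjusted Prescott/CMH test used for ease of use.
- Mark the formal-analysis column for errors in Table 5 and retitle Table 2.46 as a summary and analysis.
- State that pairs are subjects assessed on both devices, with naivety judged on use of either device in the 6 months before Visit 2 and study-assigned use excluded. List subjects assessed on one device separately.
- Note that the any-error comparison depends partly on unequal checklist lengths, so the critical-error comparison is the more interpretable one.

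**Minimum, if the endpoint is meant to be descriptive.** Remove inhaler errors from the SAP 2.4 list, exempt them from the branch that covers every other endpoint after superiority, say that the endpoint is descriptive, and still report the paired difference with its 95% CI.

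**Cost.** A short SAP edit and reuse of the ease-of-use program on two binary variables, plus the paired difference and its interval. No new data are needed. The preferred option adds two p-values to the 'other' endpoints, each read at 0.05.
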